8.1 Nivolumab (NSC 748726)

8.1.1 Other Names

BMS-936558, MDX1106, Opdivo™

8.1.2 Classification

Anti-PD-1MAb

8.1.3 Mode of Action

Nivolumab targets the programmed death-1 (PD-1, cluster of differentiation 279 [CD279]) cell surface membrane receptor. PD-1 is a negative regulatory receptor expressed by activated T and B lymphocytes. Binding of PD-1 to its ligands, programmed death-ligand 1 (PD-L1) and 2 (PD-L2), results in the down-regulation of lymphocyte activation. Nivolumab inhibits the binding of PD-1 to PD-L1 and PD-L2. Inhibition of the interaction between PD-1 and its ligands promotes immune responses and antigen-specific T-cell responses to both foreign antigens as well as self-antigens.

Rev. Add4

8.1.4 Description

Nivolumab Injection is a clear to opalescent, colorless to pale yellow liquid; light (few) particulates may be present. The drug product is a sterile, nonpyrogenic, single-use, isotonic aqueous solution formulated in sodium citrate dihydrate, sodium chloride, mannitol, diethylenetriaminepentacetic acid (pentetic acid), polysorbate 80 (Tween® 80), and water for injection. Dilute solutions of hydrochloric acid and/or sodium hydroxide may be used for pH adjustment (pH 5.5-6.5).

Rev. Add4

8.1.5 Storage and Stability

Vials of Nivolumab injection must be stored at 2°-8°C (36°-46°F) and protected from light, freezing, and shaking. The unopened vials can be stored at room temperature (up to 25°C, 77°F) and room light for up to 48 hours.

If a storage temperature excursion is identified, promptly return Nivolumab to 2°C-8°C and quarantine the supplies. Provide a detailed report of the excursion (including documentation of temperature monitoring and duration of the excursion) to [contact] for determination of suitability.

Shelf-life surveillance of the intact vials is ongoing.

If not used immediately, the infusion solution may be stored up to 24 hours in a refrigerator at 2°-8°C (36°-46°F) and a maximum of 8hours of the total 24 hours can be at room temperature (20°-25°C, 68°-77°F) and room light. The maximum 8-hour period under room temperature and room light conditions includes the product administration period.

CAUTION: The single-use dosage form contains no antibacterial preservative or bacteriostatic agent. Therefore, it is advised that the product be discarded 8 hours after initial entry.

8.1.6 Dose Specifics

Refer to Section [5.1](#) for specific dosing of nivolumab

8.1.7 Preparation

Nivolumab injection can be infused undiluted (10 mg/mL) or diluted with 0.9% Sodium Chloride Injection, USP or 5% Dextrose. When the dose is based on patient weight (i.e., mg/kg), nivolumab injection can be infused undiluted or diluted to protein concentrations as low as 0.35 mg/mL. When the dose is fixed (eg, 240 mg, 360 mg, or 480 mg flat dose), nivolumab injection can be infused undiluted or diluted so as not to exceed a total infusion volume of 160 mL. For patients weighing less than 40 kilograms (kg), the total volume of infusion must not exceed 4 mL per kg of patient weight. During drug product preparation and handling, vigorous mixing or shaking is to be avoided.

Rev. Add1
Rev. Add4

8.1.8 Route of Administration

Intravenous infusion over 30 minutes. Do not administer as an IV push or bolus injection. See Section [5.1](#)

Rev. Add4

8.1.9 Availability

Nivolumab is an investigational agent supplied to investigators by the Division of Cancer Treatment and Diagnosis (DCTD), NCI.

Nivolumab is provided to the NCI under a Collaborative Agreement between the Pharmaceutical Collaborator and the DCTD, NCI (see [Appendix IV](#)).

Nivolumab is supplied as 100 mg vials (10 mg/mL) with a 0.7mL overfill, in 10 mL type I flint glass vials, with fluoropolymer film-laminated rubber stoppers and aluminum seals.

8.1.10 Side Effects

See Section [5.3](#)

8.1.11 Nursing/Patient Implications

Rev. Add1

No incompatibilities between Nivolumab injection and polyvinyl chloride (PVC), non-PVC/non-DEHP (di[2-ethylhexyl]phthalate) IV components, or glass bottles have been observed.

Administer through a 0.2 micron to 1.2 micron pore size, low-protein binding (polyethersulfone membrane) in-line filter. Do not co-administer other drugs through the same intravenous line. The infusion line should be flushed as per institution guidelines after completion of the infusion to ensure the entire dose was administered.

8.2 Cisplatin

8.2.1 Other Names

Cisdiaminedichloroplatinum, Cis-diaminedichloroplatinum (II), diaminedichloroplatinum, cis-platinum, platinum, Platinol, Platinol-AQ, DDP, CDDP, DACP, NSC 119875.

8.2.2 Classification

Cytotoxic chemotherapy, alkylating agent

8.2.3 Mode of Action

Inhibits DNA synthesis by forming inter- and intra-strand crosslinks. Other possible mechanism include chelation of DNA and binding to cell membranes thereby stimulating immune mechanisms.

8.2.4 Storage and Stability

Intact vials of cisplatin are stored at room temperature. Protect unopened container from light. Refer to the cisplatin package insert for stability of the infusion solution after prepared. Due to the risk of precipitation, cisplatin solutions should **not** be refrigerated.

8.2.5 Dose Specifics

Refer to Section [5.1](#) for specific cisplatin dosing.

8.2.6 Preparation

Cisplatin to be mixed per institutional standard.

8.2.7 Route of Administration

Intravenous

8.2.8 Incompatibilities

Amsacrine, cefepime, gallium nitrate, mesna, piperacillin, sodium bicarbonate, thiotepa. Cisplatin may react with aluminum which is found in some syringe needles or IV sets, forming a black precipitate.

Compatibilities:

Admixture: Amphotericin-B, aztreonam, carmustine, cefazolin, cephalothin, droperidol, etoposide, floxuridine, hydroxyzine, ifosfamide, leucovorin, magnesium sulfate, mannitol, potassium chloride. Y-site: Allopurinol, bleomycin chlorpromazine, cimetidine,

cyclophosphamide, dexamethasone, diphenhydramine, doxapram, doxorubicin, famotidine, filgrastim, fludarabine, fluorouracil, furosemide, ganciclovir, heparin, hydromorphone, lorazepam, melphalan, methotrexate, methylprednisolone, metoclopramide, mitomycin, morphine, ondansetron, paclitaxel, prochlorperazine, ranitidine, sargramostim, vinblastine, vincristine, vinorelbine.

Consult your pharmacist regarding specific concentrations.

8.2.9 Availability

Commercially available as a 1 mg/mL solution in 50, 100, and 200 mg vials.

8.2.10 Side Effects

Please refer to the package insert for a comprehensive list of adverse events.

8.2.11 Nursing/Patient Implications

8.2.11.1 Monitor CBC, platelet count, BUN and creatinine prior to drug administration.

8.2.11.2 Monitor for signs of ototoxicity or neurotoxicity.

8.2.11.3 Symptom management of expected nausea and vomiting. Ondansetron (or other 5HT3 antagonist) and dexamethasone will be given daily prior to chemotherapy administration. Additional antiemetics may be provided per physician discretion.

If the treating physician chooses to use Aprepitant, when given once daily for 14 days as a 100 mg capsule with an oral contraceptive containing 35 mcg of ethinyl estradiol and 1 mg of norethindrone, this decreased the AUC of ethinyl estradiol by 43% and decreased the AUC of norethindrone by 8%. Women of childbearing potential using pregnancy contraception that includes ethinyl estradiol should not receive Aprepitant for the treatment of nausea/delayed emesis. Patients may change to a different method of contraception if they wish to use Aprepitant.

8.2.11.4 Pre- and post-treatment hydration may be administered per institutional standards.

8.2.11.5 Diuretics may be ordered as needed per physician discretion.

8.2.11.6 Use of granulocyte colony stimulating factors are permitted.

8.2.11.7 Observe for signs of allergic reaction.

8.3 Carboplatin

8.3.1 Other Names

Paraplatin®

8.3.2 Classification

Carboplatin (carboplatin injection) (platinum, diammine[1,1-cyclobutanedicarboxylato(2-)O,O']-, (SP-4-2)) is a platinum coordination compound, used as an anti-neoplastic agent. It is a second-generation tetravalent organic platinum compound. It is a crystalline powder with the molecular formula of C₆H₁₂N₂O₄Pt and a molecular weight of 371.25. It is soluble in water at a rate of approximately 14 mg/mL, and the pH of a 1% solution is 5 to 7. It is virtually insoluble in ethanol, acetone, and dimethylacetamide.

8.3.3 Mode of Action

Like cisplatin, carboplatin binds to DNA, thereby inhibiting DNA synthesis, in a cell cycle nonspecific manner. Carboplatin must first undergo activation to produce antineoplastic activity. Bidentate carboxylate ligands of carboplatin are displaced by water forming (aquation) positively charged platinum complexes, which bind to nucleophilic sites in DNA, such as the O-6 position on guanine. Carboplatin produces predominantly interstrand DNA crosslinks rather than DNA-protein crosslinks. Intrastrand crosslinks result from the formation of adducts between the activated platinum complexes of the drug and the N-7 atom (not exclusively) atom on guanine to produce 1,2 intrastrand links between adjacent guanine molecules, between neighboring guanine and adenine molecules, or between neighboring guanine molecules. Interstrand cross-linking within the DNA helix also occurs. Platinum adducts may inhibit DNA replication, transcription and ultimately cell division.

8.3.4 Storage and Stability

Store intact vials at room temperature at 25°C (77°F); excursions permitted to 15°C to 30°C (59°F to 86°F). Protect from light. Further dilution to a concentration as low as 0.5 mg/mL is stable at room temperature (25°C) for 8 hours in NS or D₅W. Stability has also been demonstrated for dilutions in D₅W in PVC bags at room temperature for 9 days; however, the manufacturer recommends use within 8 hours due to lack of preservative. Multidose vials are stable for up to 14 days after opening when stored at 25°C (77°F) following multiple needle entries.

Rev. Add1
Rev. Add3

8.3.5 Dose Specifics

See Section [5.1](#) for specific carboplatin dosing.

Calvert Formula for Carboplatin (AUC) Dosing

Total dose (mg) = target AUC (in mg x mL/minute) x [*GFR (in mL/minute) + 25]

For the purposes of this protocol, the GFR is considered to be equivalent to the creatinine clearance.

Glomerular Filtration Rate (GFR)* Estimation: Calculated creatinine clearance of ≥ 50 cc/min using the Cockcroft-Gault formula:

Males:
$$\frac{(140 - \text{Age in years}) \times \text{Actual Body Weight in kg}}{72 \times \text{Serum Creatinine (mg/dL)}}$$

Females: Estimated creatinine clearance for males $\times 0.85$

With the Calvert formula, the total (final) dose of carboplatin is calculated in mg, not mg/m².

The minimum serum creatinine value used will be 0.7 mg/dL and a CrCl cap will be 125 mL/min.

Questions about this calculation should be directed to the principal investigator.

8.3.6 Preparation

Manufacturer's labeling states solution can be further diluted to concentrations as low as 0.5 mg/mL in NS or D₅W; however, most clinicians generally dilute dose in either 100 mL or 250 mL of NS or D₅W. Concentrations used for desensitization vary based on protocol. Hazardous agent; use appropriate precautions for handling and disposal. Needles or IV administration sets that contain aluminum should not be used in the preparation or administration of carboplatin; aluminum can react with carboplatin resulting in precipitate formation and loss of potency.

8.3.7 Route of Administration

Intravenous

8.3.8 Incompatibilities

Amphotericin B cholesteryl sulfate complex. Aluminum reacts with carboplatin causing precipitate formation and loss of potency; therefore, needles or intravenous sets containing aluminum parts that

Rev. Add4

may come in contact with the drug must NOT be used for the preparation or administration of carboplatin.

8.3.9 Availability
Carboplatin (Bristol-Myers Oncology Division) is commercially available as a 10 mg/mL solution in 50, 150, 450, and 600 mg vials.

8.3.10 Side Effects
Please refer to the package insert for a comprehensive list of adverse events.

8.3.11 Nursing/Patient Implications

- 8.3.11.1 Monitor CBC and platelet count; nadir occurs at approximately day 21 with recovery by day 28-30.
- 8.3.11.2 Premedicate with antiemetics—evaluate effectiveness. Ondansetron (or other 5HT3 antagonist) and dexamethasone are required.
- 8.3.11.3 Monitor fluid status—maintain adequate hydration. Pre- and post-treatment hydration may be administered per institutional standards.
- 8.3.11.4 Assess skin/mucous membranes.
- 8.3.11.5 Assess for signs of peripheral neuropathy—coordination, sensory loss.

8.4 Etoposide

8.4.1 Other Names
VP-16, VePesid, VP-16-213, EPEG, epipodophyllotoxin, NSC # 141540.

8.4.2 Classification
Cytotoxic chemotherapy, podophyllotoxin derivative.

8.4.3 Mode of Action
Etoposide inhibits the enzyme topoisomerase II, nucleoside transport and incorporation, and causes DNA breakage.

8.4.4 Storage and Stability
The vials should be stored at room temperature. Following dilution in 0.9% sodium chloride or 5% dextrose to concentrations of 0.2-0.4

mg/mL the drug is chemically stable for 96 and 24 hours at room temperature respectively. Bristol-Myers in-house data indicate that etoposide may be stable in 5% dextrose or normal saline for 24 hours (0.6 mg/mL), 4 hours (1 mg/mL), and 2 hours (2 mg/mL).

8.4.5 Dose Specifics

Refer to Section [5.1](#) for specific etoposide dosing.

8.4.6 Preparation

Etoposide to be prepared per institutional standard.

8.4.7 Route of Administration

Intravenous

8.4.8 Incompatibilities

Please refer to the etoposide prescribing information for more detailed information regarding incompatibilities.

8.4.9 Availability

Commercially available

Etoposide is commercially available as a 20 mg/mL solution in 100 mg, 500 mg and 1 gm vials.

8.4.10 Side Effects

Please refer to the package insert for a comprehensive list of adverse events.

8.4.11 Nursing/Patient Implications

8.4.11.1 Monitor CBC and platelet count prior to drug administration.

8.4.11.2 Advise patient of possible alopecia. Instruct how to obtain wig, hairpiece, etc.

8.4.11.3 Observe for possible phlebitis at injection site or burning pain with infusion.

8.4.11.4 Monitor for rare anaphylactoid reaction.

8.4.11.5 Administer antiemetics as indicated.

9.1 Study Design and Objectives

This is a randomized phase II clinical trial comparing etoposide combined with a choice of platinum-based therapy (carboplatin or cisplatin; CE) with or without nivolumab (CEN) in patients with previously untreated extensive stage SCLC.

The primary objective of the trial is to determine whether combination therapy including nivolumab extends progression-free survival (PFS) for this patient population. Secondary objectives include estimation of overall survival, best objective response, and toxicity with first line therapy. Correlative endpoints include evaluation of PD-L1 expression in archival tumor tissues and other serum biomarkers in relation to clinical outcome.

9.2 Study Endpoints

PFS is defined as the time from randomization to documented disease progression or death from any cause, whichever occurs first. Patients who have not experienced an event of interest by the time of analysis will be censored at the date they are last known to be alive and progression-free. Overall survival is defined as the time from randomization to death from any cause, and patients who are thought to be alive at the time of final analysis will be censored at the last date of contact. Best objective response will be evaluated via RECIST1.1 criteria. Toxicity will be determined using the CTCAE criteria. IHC positivity is defined as positive membrane staining in more than 1% of viable tumor cells among a minimum of 100 evaluable tumor cells.

9.3 Statistical Analysis Plan

The primary and some secondary analyses will include all eligible and treated patients. Exception to this include: analysis of toxicity data, which will include all patients who received study drug regardless of eligibility, and analyses of response, which will include eligible and treated patients with measurable disease. Time-to-event data, such as PFS and OS, will be estimated using the Kaplan-Meier method, and Cox proportional hazards models will be used to estimate the treatment hazard ratios. The primary comparison of PFS will use a logrank test stratified on the randomization stratification factors with a one-sided type I error rate of 10%. Other comparisons of groups will be made using the log rank test and Cox modeling. Categorical data, such as response rates (CR+PR) and toxicity, will be compared using Fisher's exact tests with a one-sided type I error rate of 10%; multivariable logistic regression modeling will be used to adjust for the effect of any covariates that are associated with these categorical outcomes. Continuous outcomes will be analyzed using Wilcoxon rank sum test, and multivariable linear regression models may be used to adjust for multiple associations with outcome.

Modeling procedures will implement backward selection; variables significant at the 0.10 level in the univariate setting will be chosen for inclusion in an initial full model, and at each step the least significant variable will be removed from the model. Only those covariates with $p < 0.05$ will remain in any final models, unless there are factors identified by the study team as crucial to model interpretation.

Point estimates of all endpoints will be accompanied by the corresponding 95% confidence intervals; however, 80% confidence intervals will also be provided for

the primary endpoint (PFS) hazard ratio. In the event that there are missing data, no imputation of the missing data will be conducted. We will assume that data are missing at random and will conduct all analyses as originally planned because we do not anticipate an excess of missing data.

Subset analyses are planned for all stratification factors and all known prognostic factors, such as performance status, age, sites of metastases, gender, etc. Subset analyses of all variables, including correlatives, are considered to be exploratory in nature.

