NOTE: The status given only reflects compliance with IRB documentation and institutional compliance with protocol-specific requirements outlined by the Lead Network. It does not reflect compliance with protocol requirements for individuals participating on the protocol or the enrolling investigator's status with the NCI or their affiliated networks.

Patient Enrollment

Patients must not start protocol treatment prior to registration.

Treatment should start within seven working days after registration.

Patient enrollment will be facilitated using the Oncology Patient Enrollment Network (OPEN). OPEN is a web-based registration system available on a 24/7 basis. To access OPEN, the site user must have an active CTEP-IAM account (check at <https://ctepcore.nci.nih.gov/iam>) and a 'Registrar' role on either the LPO or participating organization roster. Registrars must hold a minimum of an AP registration type.

All site staff will use OPEN to enroll patients to this study. It is integrated with the CTSU Enterprise System for regulatory and roster data and, upon enrollment, initializes the

patient in the Rave Database. OPEN can be accessed at <https://open.ctsu.org> or from the OPEN tab on the CTSU members' side of the website at <https://www.ctsu.org>. To assign an IVR or NPIVR as the treating, crediting, consenting, drug shipment (IVR only), or investigator receiving a transfer in OPEN, the IVR or NPIVR must list on their Form FDA 1572 in RCR the IRB number used on the site's IRB approval.

Prior to accessing OPEN, site staff should verify the following:

- All eligibility criteria have been met within the protocol stated timeframes, including verifying availability of tumor tissue as per eligibility criteria.
- All patients have signed an appropriate consent form and HIPAA authorization form (if applicable).

NOTE: The OPEN system will provide the site with a printable confirmation of registration and treatment information. Please print this confirmation for your records.

Further instructional information is provided on the OPEN tab of the CTSU members' side of the CTSU website at <https://www.ctsu.org> or at <https://open.ctsu.org>. For any additional questions contact the CTSU Help Desk at [name] or [contact].

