9.4 Sample Size Considerations

The primary comparison will include all eligible and treated patients, of whom 135 will be accrued and randomized equally, for a total accrual of 67 patients per arm. After adjusting for an ineligibility rate of 10%, the total required sample size for randomization is 150 patients. Using an overall one-sided 0.10 level log rank test, this study will have 88% power to detect a 37.5% reduction in the PFS hazard rate of 0.139 to 0.087 based on the estimated accrual and follow-up period. Assuming an exponential survival, this corresponds to a 60% improvement in the median PFS of 5 months on CE to 8 months on CE plus nivolumab. The number of PFS events needed to achieve this power is 113 events under the alternative hypothesis.

Correlative Study Statistical Considerations:

Tumor DNA levels obtained from the serial collection of cfDNA samples will be examined to explore whether clinical outcome is associated with fluctuations in DNA levels following the administration of therapy. Plasma will be collected from 30 patients on each arm of the study at baseline and cycle 2 day 1.

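### The primary PFS test, and by elimination OS, drops randomised patients who never start treatment in a trial where the arm is known before the first dose, and no all-randomised analysis is planned as a check.

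*Combined protocol and SAP*

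**What the plan says.** Section 9.3 sets the population: "The primary and some secondary analyses will include all eligible and treated patients". The exceptions it names are toxicity (everyone who received study drug) and response (eligible, treated, measurable disease). Section 9.4 restates the set for the primary test: "The primary comparison will include all eligible and treated patients, of whom 135 will be accrued and randomized equally". The only inflation is for ineligibility: "After adjusting for an ineligibility rate of 10%, the total required sample size for randomization is 150 patients".

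No sentence assigns OS a population. Section 9.1 lists the secondary objectives: "Secondary objectives include estimation of overall survival, best objective response, and toxicity with first line therapy". Two of these three have their own set in 9.3, which leaves OS in the eligible-and-treated set.

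Section 9.2 starts both clocks at randomisation: "PFS is defined as the time from randomization to documented disease progression or death from any cause, whichever occurs first"; "Overall survival is defined as the time from randomization to death from any cause".

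On timing, the Patient Enrollment text in Section 4 says: "Treatment should start within seven working days after registration". On what the site knows by then: "The OPEN system will provide the site with a printable confirmation of registration and treatment information". Section 5.1 lists no placebo in Arm B, and no blinding is described.

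Section 4.7 requires baseline and follow-up data on patients who never start. Sections 5.7 and 7.1 (footnote 12) follow all patients to progression and for survival. Section 9 does not use the never-started patients in any efficacy analysis.

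**The concern.** Randomisation protects a comparison of the groups as randomised. Here, entry to the primary analysis depends on a later event, the first dose, that occurs after patient and site can know the arm. A patient who hoped for nivolumab and drew control may leave before dosing. If the chance of leaving differs by arm and is related to prognosis, the treated-only groups are no longer comparable, and the PFS and OS hazard ratios carry the difference. Nothing planned would reveal it. The result matters beyond this trial, because Section 1.4 presents a positive outcome as the rationale for a phase III trial.

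Excluding ineligible patients is the lesser issue. Section 3 and the checks before OPEN tie eligibility to facts fixed before registration. What is missing there is a statement that the final eligibility decision is made without knowledge of arm or outcome.

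**Working it through.** **1. The plan's own figures.** Inputs from 9.4 and 9.5: one-sided alpha 0.10 (z = 1.2816), medians 5 and 8 months, HR 0.625, 113 events, 135 analysed of 150 randomised, 15 months of accrual plus 10 of follow-up.

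- Power = Φ(√d/2 × |ln HR| − z) = Φ(√113/2 × 0.470 − 1.2816) = Φ(1.217) = 88.8% (plan: 88%).
- Expected events per arm = n[1 − (e^(−λF) − e^(−λ(A+F)))/(λA)], with n = 67.5, A = 15, F = 10. Control (λ = 0.1386) gives 60.4 and nivolumab (λ = 0.0866) gives 51.6, total 112.0 (plan: 113).
- 150 × 0.90 = 135.

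The design arithmetic is sound. The issue is only who is analysed.

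**2. Type I error of the treated-only test.** The documents give no never-treated rate, so the loss rates and leaver hazards are assumptions. The simulation used 40,000 trials per scenario (Monte Carlo standard error 0.1–0.2 points), 75 per arm, uniform accrual over 150/9 = 16.7 months plus 10 months, and exponential PFS with median 5 months in both arms. The leaver type was equally common in both arms. The log-rank test was stratified on four equal, non-prognostic strata. Loss in the control arm only, one-sided error in % (nominal 10):

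| Control loss | Leavers at 0.5 × hazard | 0.75 × | 1.5 × | 2 × |
|---|---|---|---|---|
| 2% (1–2 of 75) | 11.6 | 10.7 | – | – |
| 5% (about 4) | 14.1 | 11.7 | 8.7 | 7.4 |
| 10% (7–8) | 18.9 | 13.6 | 7.3 | 5.8 |

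(– : not computed.)

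- At half the hazard, the mean HR under no effect is 0.985, 0.96 and 0.93 for 2%, 5% and 10% loss.
- Loss of 5% in control against 2% in nivolumab gives 12.4% (half hazard) or 11.1% (0.75 times).
- Equal 5% loss in both arms gives 10.3%.

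**3. The same trials, all randomised patients.** With full follow-up the error is 9.8–10.4% in every case. If half of the never-treated withdraw on day 0, it is 11.8% and 13.9% in the 5% and 10% half-hazard cases. The excess over 10 then falls from 4.1 to 1.8 points and from 8.9 to 3.9 points.

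**4. A different prognosis model.** Half the patients have median PFS 7 months and half 3.5; 3, 5 or 8 control patients leave; 20,000 trials per case, unstratified, 15 + 10 months.

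- Better-prognosis leavers: 11.5%, 13.1%, 14.4%.
- Worse-prognosis leavers: 9.1%, 7.9%, 6.9%.
- Random leavers: about 10%.
- All-randomised test: 9.7–10.5% throughout.

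**5. Power.** If never-treated loss of 2%, 5% or 10% comes on top of 10% ineligibility, the current primary set falls to 132, 128 or 122 patients, with power 88.1%, 87.3% or 85.9%.

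For an all-randomised primary analysis, 150 patients give 121.5 events at month 25 or 126.0 at 10 months after last entry. If a fraction f has no treatment effect, ln HR is scaled by (1 − f), which is an approximation:

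| f | Planned time | At exactly 113 events |
|---|---|---|
| 0 | 90–91% | 89% |
| 5% | 88–89% | 86% |
| 10% | 85–86% | 83% |

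**The case against.** **The rule is open and consistent.** The set is named in both 9.3 and 9.4, the 135 used for power is that set, and this is a phase II screen at one-sided 10%. That can defend the primary choice. It does not explain the absence of any check.

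**The larger figures need strong assumptions.** Half the hazard means leavers with median PFS of 10 months, when Section 1.1 puts median survival on platinum-etoposide at 9–11 months. At 0.75 times the hazard and 2–5% loss, the excess is only 0.7–1.7 points. This stands: 18.9% is an upper illustration, not an expectation.

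**The direction may be conservative.** In a fast-progressing disease, patients may fail to start because they deteriorate. If those losses are in the control arm only, the error falls below 10%. This also stands, although the direction reverses if the sicker leavers are in the nivolumab arm.

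**OS is an inference.** The wording about some secondary analyses and exceptions need not be exhaustive. Granted; but then the OS population is unstated, which the same edit repairs.

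**The 10% may be meant as total attrition.** The step from 150 to 135 eligible and treated can be read that way, though the text names only ineligibility. Even a further 10% loss leaves about 86% power, so this is minor.

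**Follow-up of never-started patients may be thin.** Section 4.7 defers their schedule to the Forms Completion Guidelines, and footnote 12 counts from stopping treatment or ending observation, which does not fit someone who never began. Protection may therefore be partial, as step 3 shows.

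**Conclusion.** The concern holds and should be fixed. The plan conditions its primary comparison on an event after randomisation that can depend on a known allocation, and it plans no analysis that would expose the effect. Bias requires both that never-starting differs by arm and that it is related to prognosis; with equal loss, or loss unrelated to prognosis, nothing is distorted. In the scenarios examined with unequal loss, the nominal 10% error ranges from 5.8% to 18.9%, and from 10.7% to 11.7% for 2–5% control-only loss at 0.75 times the hazard. All of these rest on assumed rates and hazards. Confidence is high in the omission; its consequence in this trial cannot be known from the documents.

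**What to change.** In Section 9.3:

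- Pre-specify a PFS and OS analysis of all randomised patients in their assigned arm, with the same stratified log-rank and Cox methods, as a named sensitivity analysis reported beside the primary hazard ratio.
- State the OS population explicitly.
- Report never-started and ineligible patients by arm, with reasons.
- State that the final eligibility decision is made without knowledge of arm or outcome.

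Toxicity stays on treated patients. It is also worth confirming that the Forms Completion Guidelines carry never-started patients to progression and survival, since the sensitivity analysis depends on it.

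The cost is a few sentences and one more run of the same models. No patients are added, the stated 88% power is unchanged, and the follow-up is already called for in 4.7, 5.7 and 7.1. The drawbacks are possible dilution of the effect and only partial protection if never-treated patients withdraw early.

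Making the all-randomised set primary would be stronger but is a trade-off. Section 9.4 would then need its power restated along the lines of step 5.
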